6.5 Pharmacokinetic (PK) Analysis Set

The Pharmacokinetic (PK) analysis set will include all subjects who received at least one dose of IMP, and have at least one post-dose evaluable plasma concentration.

6.6 Definition of Completed Subjects

The treatment period is defined as the time period during which subjects are evaluated for primary and secondary objectives of the trial irrespective of whether or not the subject actually takes all doses of the IMP. Subjects who are evaluated at the last scheduled visit during the treatment period will be defined as trial completers. For purposes of this trial, subjects in Part 1 who complete the last scheduled PK assessment on Day 26 and subjects in Part 2 who complete the last scheduled PK assessment on Day 32 will be defined as trial completers.

6.7 Definition of Baseline

In both parts 1 and 2, baseline will be the last available value prior to the start of IMP treatment.

Quabodepistat (OPC-167832)

Study 323-201-00007

For clinical laboratory data, see [Section 10.3](#). For vital sign measurements, see [Section 10.4](#). For ECGs, please see [Section 10.6](#). For C-SSRS, see [Section 10.7](#).

6.8 Handling of Missing Data

No data imputation will be performed for missing PK and safety data in this trial. The handling of concentrations below the lower limit of quantification will be according to the sponsor's data handling processes for PK data.

6.8.1 Incomplete Dates

Unless otherwise stated in the analysis sections (eg, AE and concomitant medication), the general rule for imputing incomplete dates when the year is present is to use January if only the month is missing and the first day of a month if only the day is missing, provided these dates are consistent with existing dates within the data and are chronologically consistent. If both month and day are missing, but the year is available, 01 Jan is imputed. If the year is unknown, the date will be considered as missing.

7 Primary and Secondary Outcome Variables

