8.5 Prior and Concomitant Medication

The investigator will record all medications (including prescription medications, over-the-counter medications, herbal remedies, vitamins and supplements, etc) and therapies taken by the subject from 30 days prior to first dose of IMP through the end of the evaluation period (defined as the time period during which subjects are evaluated for primary and/or secondary objectives) in the eCRF. The investigator will also record all medications and therapies taken by the subject for treatment of an AE or which caused an

Quabodepistat (OPC-167832)

Study 323-201-00007

AE until the end of the trial (defined as the last date of contact or date of final contact attempt) in the eCRF.

Medications taken other than IMP will be coded using the WHO drug dictionary (WHODrug 3BG, 01 Mar 2022 or later version) and will be presented separately for each Part.

The proportion of subjects taking concomitant medications will be tabulated for the safety analysis set in the periods prior to, during and after the trial medication.

In addition, listings of concomitant medications will be provided.

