10.2 Adverse Events

All AEs will be coded by Medical Dictionary for Regulatory Activities (MedDRA, Version 25 or a later version if available).

Treatment-emergent adverse events (TEAEs) are defined as AEs with an onset date on or after the start of IMP treatment. TEAEs are all AEs which started after the start of IMP treatment; or if the event was continuous from baseline and worsens either in intensity or frequency, becomes serious, is assessed as IMP-related or results in death.

Relatedness of AEs to IMP will be collected for each IMP, individually, OPC 167832 and itraconazole for Part 1 and OPC 167832 and carbamazepine for Part 2.

A Serious Adverse Event (SAE) includes any event that results in any of the following outcomes:

- Death.
- Life-threatening; ie, the subject was, in the opinion of the investigator, at immediate risk of death from the event as it occurred. It does not include an event that, had it occurred in a more severe form, might have caused death.
- Persistent or significant incapacity/disability or substantial disruption of the ability to conduct normal life functions.
- Requires inpatient hospitalization or prolongs hospitalization.
Hospitalization itself should not be reported as an SAE; whenever possible the reason for the hospitalization should be reported.
 - Hospitalizations or prolonged hospitalizations for social admissions (ie, those required for reasons of convenience or other nonmedical need) are not considered SAEs.
 - Prescheduled hospitalization to address a condition that has existed prior to the signing of the ICF should not be considered an SAE and should be recorded as medical history.
- Congenital anomaly/birth defect.

Quabodepistat (OPC-167832)

Study 323-201-00007

- Other medically significant events that, based upon appropriate medical judgment, may jeopardize the subject and may require medical or surgical intervention to prevent one of the outcomes listed above, eg, allergic bronchospasm requiring intensive treatment in an emergency room or home, blood dyscrasias or convulsions that do not result in hospitalization, or the development of drug dependency or drug abuse.

Nonserious AEs are all AEs that do not meet the criteria for a “serious” AE.

The frequency and percentage of subjects with the following events, together with the number of events, (events listed below), will be summarized by SOC, MedDRA preferred term, severity, and treatment for each of Part 1 and Part 2 separately

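### SAP 6.8.1 defers to partial-date rules for adverse events and concomitant medication that SAP 10.2 and 8.5 do not contain, and the first-of-month default can date a post-dose event before dosing or before the combination period

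*SAP*

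**What the plan says.** SAP 6.8.1 opens with a deferral: "Unless otherwise stated in the analysis sections (eg, AE and concomitant medication), the general rule for imputing incomplete dates". The rule itself is to "use January if only the month is missing and the first day of a month if only the day is missing", and 1 January is used when only the year is known. It does not separate start dates from stop dates. A proviso follows: "provided these dates are consistent with existing dates within the data and are chronologically consistent". Nothing says what to do when the proviso fails.

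The parent section, SAP 6.8, states: "No data imputation will be performed for missing PK and safety data in this trial". Protocol 9.3 says the same.

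SAP 10.2 makes onset date the test for treatment emergence: "Treatment-emergent adverse events (TEAEs) are defined as AEs with an onset date on or after the start of IMP treatment". A second limb keeps an event continuous from baseline as a TEAE if it worsens, or if it "becomes serious, is assessed as IMP-related or results in death". The section summarises AEs by treatment and also provides all-AE summaries and a full listing. It has no rule for incomplete dates.

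SAP 8.5 tabulates concomitant medications "in the periods prior to, during and after the trial medication". It has no date rule either.

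**The concern.** The SAP signals that AEs and concomitant medications may need their own date rules and then supplies none. The general rule therefore applies, and it always picks the earliest date the known parts allow. For AE onset that is the unfavourable direction: an event can move from after dosing to before it, or from the combination period to an earlier one, but never the other way.

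The proviso does not clearly prevent this. It names no reference date. Protocol 8.6.2 starts AE collection at consent and screening runs from Day -28 to Day -2, so an imputed date between consent and Day 1 contradicts nothing.

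At stake is the secondary objective, safety of OPC-167832 alone and in combination. With 12 subjects per part, one subject with an event is 1/12 = 8.3 percentage points.

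**Working it through.** The plan states no figure on this point, so there is none to reproduce. The mechanism can be followed in the text and then sized by counting calendar dates.

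**Example.** A Part 1 subject has Day 1 on 10 March, and an AE that really began on 20 March is recorded with the day missing. The rule gives 1 March, nine days before dosing. Screening for this subject runs from 10 February (Day -28) to 8 March (Day -2) in a non-leap year. If consent was on or before 1 March (20 of the 27 possible dates), the imputed date lies between consent and first dose and conflicts with neither. If consent was on 2 to 8 March, the imputed date precedes consent and the proviso could reject it, but no replacement is given.

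**Inputs from the documents.** Screening Day -28 to Day -2; clinic stay to Day 26 (Part 1) or Day 32 (Part 2); follow-up call about Day 45 or Day 55 (Protocol 1.1, Trial Duration). Combination dose on Day 15 or Day 25 (SAP Table 3.2-1).

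**Assumptions not in the documents.** Day 1 is equally likely on each of 365 dates, consent on each of Day -28 to Day -2, and true onset on each day of the stated range. Only the day of the month is missing.

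**Method.** For each combination, replace the onset date by the first of its month. Count it as pre-dose if that date is before Day 1. In the restricted count, require also that it is not before consent.

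| True onset | Dated before Day 1, no consent check | Dated before Day 1, dates before consent blocked |
|---|---|---|
| Same calendar month as Day 1 (Part 1 to Day 45, Part 2 to Day 55) | 93.6% | 64.0% |
| Part 1, Days 1-26 | 55.6% | 37.7% |
| Part 1, Days 1-45 | 32.7% | 22.4% |
| Part 2, Days 1-55 | 26.8% | 18.3% |
| Part 1, Days 27-45 (after discharge) | 1.4% | 1.4% |
| Part 2, Days 33-55 (after discharge) | 0% | 0% |

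The last row is exactly zero because Day 33 can never fall in the calendar month of Day 1. In Part 1, an onset after discharge is misdated before Day 1 only if Day 1 falls on the 2nd to the 5th of a month.

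Most of the Part 1 figure for Days 1-45 comes from the inpatient days: 0.556 × 26/45 = 0.321 of the 0.327. In Part 2 all of it does.

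**Period shift after discharge.** The same count compares the imputed date with the combination dose. In Part 1 (Days 27-45), 27.8% are dated before Day 15; removing the 1.4% dated before Day 1 leaves 26.4% that stay TEAEs but fall in an earlier period. In Part 2 (Days 33-55), 34.4% are dated before Day 25 and all stay TEAEs. These figures matter only if treatment is assigned by onset date. SAP 10.2 says only that summaries are by treatment and gives no other basis.

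**The case against.** A reader might infer that any AE with a missing onset day is automatically dated before first dose and drops out. The documents do not support that. The rule is a general one with a proviso. It does no harm when Day 1 is the first of the month, and an onset in a later month is still dated after first dose. Reading the proviso as blocking dates before consent lowers 94% to 64%; reading it as also protecting the first dose lowers it to zero. It simply does not say which.

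The larger percentages also come from days when a missing date is least likely. Subjects live in the clinic from Day -1 to Day 26 or Day 32, AEs are assessed on every trial day, and start dates are recorded, with times where possible. After discharge, where a partial date is most plausible, loss of TEAE status nearly vanishes.

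Safeguards exist. The second limb of the definition recovers ongoing events that worsen, become serious, are judged IMP-related or are fatal, so what is lost is mainly unrelated, nonserious events. All AEs are still summarised and listed. Given SAP 6.8 and Protocol 9.3, it is even unclear whether AE dates should be imputed at all.

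A reader might also infer that prohibited medications would go unlisted because a stop date was set to the first of the month. That is weak. A stop date imputed before a known start date fails the proviso, the listing covers the whole trial, which starts at consent, and the prohibition itself reaches back before first dose.

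All of this limits how often the problem arises. It does not supply the missing rule, define the proviso or change the direction of the error.

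**Conclusion.** The gap is real and modest. SAP 6.8.1 points to AE and medication date rules that are absent, and its default, followed literally, can turn a post-dose AE into a pre-dose one. For events in the month of first dose with only the day missing, this affects about 64% if dates before consent are blocked and 94% if they are not. After discharge, the main risk is instead the move out of the combination period, about 26% in Part 1 and 34% in Part 2, conditional on treatment being assigned by onset date.

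These are shares of events with a missing day, not of all events. They rest on uniform Day 1, consent and onset dates. The documents do not say how many partial dates to expect; in an inpatient trial there should be few. The point is worth correcting because the error runs one way, the groups are small and the remedy is cheap.

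**What to change.** In SAP 10.2:

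- Treat an AE with an incomplete onset date as treatment-emergent unless the known date parts or the stop date show onset before the first IMP dose. If the known parts match the month and year of first dose, impute the first-dose date.
- Where the treatment period is ambiguous, assign the event to the latest period consistent with the known parts, the stop date and the reporting date.

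In SAP 6.8.1 or 8.5, impute a missing stop day as the last day of the month. In SAP 6.8, make clear that the bar on imputing missing safety data does not extend to these date conventions.

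The cost is a few sentences and a small programming change. The downside is that an occasional event that really began before dosing, or in an earlier period, may be counted as treatment-emergent or attributed to the combination. For a safety summary that is the conservative direction, and the listings should show the dates as recorded so that such cases are visible.

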7.1 Primary Outcome Variables

The primary endpoints of the trial are the following PK parameters:

- maximum plasma concentration of the drug (C_{\max})
- area under the concentration-time curve calculated to the last observable concentration at time t (AUC_t)
- area under the concentration-time curve from time zero to infinity (AUC_{∞})

The effect of itraconazole or carbamazepine administration on the single-dose PK of OPC-167832 will be assessed using the above PK parameters in the presence and absence of either itraconazole (Part 1) or carbamazepine (Part 2).

7.2 Secondary Outcome Variables

Safety outcome variables for individuals will be based on

- Adverse Events
- Vital Signs and Physical Examination
- Electrocardiograms (ECGs)
- Clinical laboratory tests
- Columbia-Suicide Severity Rating Scale (C-SSRS) (for Part 2 only)

Quabodepistat (OPC-167832)

Study 323-201-00007

8 Disposition and Demographic Analysis

8.1 Subject Disposition

The number of subjects enrolled, the number of subjects who are treated, and the number of subjects who discontinue from the trial, together with the reasons for discontinuation taken from the eCRF status page, the number of completers and the number of subjects lost to follow-up, will be provided for each Part separately.

8.2 Demographic and Baseline Characteristics

Demographic and baseline characteristics will be summarized for all enrolled subjects by Part. Continuous variables (age, weight, and height) will be summarized by descriptive statistics: number of non-missing values, mean, median, standard deviation, minimum, and maximum. Categorical variables (sex, race, ethnicity, and gender) will be summarized by counts and percentages within each category. Demographic and baseline characteristics will be summarized for each Part separately.

8.3 Medical History

Listings for general medical history (coded using Medical Dictionary for Regulatory Activities [MedDRA] Version 25 or a later version, if available) based on safety analysis set will be provided for each Part.

8.4 Treatment Compliance

The date, time and dose of IMP administration during the trial will be recorded on the eCRF. Information regarding any inappropriately administered doses will also be documented on the eCRF. All doses of IMP will be administered while the subjects are in the clinic; compliance will be ensured by a mouth check during the oral dosing administration of IMP.

A listing of treatment compliance (dose administered) for each subject based on the safety analysis set will be provided for each Part.

8.5 Prior and Concomitant Medication

The investigator will record all medications (including prescription medications, over-the-counter medications, herbal remedies, vitamins and supplements, etc) and therapies taken by the subject from 30 days prior to first dose of IMP through the end of the evaluation period (defined as the time period during which subjects are evaluated for primary and/or secondary objectives) in the eCRF. The investigator will also record all medications and therapies taken by the subject for treatment of an AE or which caused an

Quabodepistat (OPC-167832)

Study 323-201-00007

AE until the end of the trial (defined as the last date of contact or date of final contact attempt) in the eCRF.

Medications taken other than IMP will be coded using the WHO drug dictionary (WHODrug 3BG, 01 Mar 2022 or later version) and will be presented separately for each Part.

The proportion of subjects taking concomitant medications will be tabulated for the safety analysis set in the periods prior to, during and after the trial medication.

In addition, listings of concomitant medications will be provided.

8.6 Prohibited Medications or Therapies

The use of prescription, over-the-counter, herbal medications, or vitamin supplements within 14 days prior to the first dose and during the treatment period of the trial are prohibited. Antibiotics or dietary supplements (eg, creatine) within 30 days prior to the first dose and during the treatment period of the trial are prohibited. Medications other than the protocol-specific trial interventions and the contraception specified in [Appendix 10.3](#) are not to be taken during the trial; however, the sponsor may allow exceptions only if the medication is unlikely to affect the PK result.

A listing of prohibited medications taken during the trial will be provided.

8.7 Lost to Follow-up

Subjects who do not complete the last scheduled PK assessment on Day 26 for Part 1 and Day 32 for Part 2 during the trial intervention period, who do not have a known reason for discontinuation (eg, withdrew consent/assent or AE), and for whom a survival status at the end of the trial cannot be determined will be classified as “lost to follow-up.”

Number of subjects lost to follow-up (LTFU) will be tabulated in the Subject Disposition table.

8.8 Protocol Deviations

Major protocol deviations, as recorded in the eCRF, will be listed.

9 Efficacy Analyses

Not applicable

10 Safety Analyses

The safety analysis will be conducted on the safety analysis set for each part separately. Safety variables to be analyzed include AEs, clinical laboratory assessments, vital signs,

Quabodepistat (OPC-167832)

Study 323-201-00007

12-lead ECGs, physical examinations, and the Columbia-Suicide Severity Rating Scale ([C-SSRS] Part 2 only). Descriptive statistics will be provided for the safety variables. Baseline measurements of safety variables are defined as the last measurement prior to the first dosing of IMP (also see [Section 6.7](#)).

10.1 Extent of Exposure

Extent of exposure to the trial medication for Safety Analysis Set will be summarized using descriptive statistics.

10.2 Adverse Events

All AEs will be coded by Medical Dictionary for Regulatory Activities (MedDRA, Version 25 or a later version if available).

Treatment-emergent adverse events (TEAEs) are defined as AEs with an onset date on or after the start of IMP treatment. TEAEs are all AEs which started after the start of IMP treatment; or if the event was continuous from baseline and worsens either in intensity or frequency, becomes serious, is assessed as IMP-related or results in death.

Relatedness of AEs to IMP will be collected for each IMP, individually, OPC 167832 and itraconazole for Part 1 and OPC 167832 and carbamazepine for Part 2.

A Serious Adverse Event (SAE) includes any event that results in any of the following outcomes:

- Death.
- Life-threatening; ie, the subject was, in the opinion of the investigator, at immediate risk of death from the event as it occurred. It does not include an event that, had it occurred in a more severe form, might have caused death.
- Persistent or significant incapacity/disability or substantial disruption of the ability to conduct normal life functions.
- Requires inpatient hospitalization or prolongs hospitalization.
Hospitalization itself should not be reported as an SAE; whenever possible the reason for the hospitalization should be reported.
 - Hospitalizations or prolonged hospitalizations for social admissions (ie, those required for reasons of convenience or other nonmedical need) are not considered SAEs.
 - Prescheduled hospitalization to address a condition that has existed prior to the signing of the ICF should not be considered an SAE and should be recorded as medical history.
- Congenital anomaly/birth defect.

Quabodepistat (OPC-167832)

Study 323-201-00007

- Other medically significant events that, based upon appropriate medical judgment, may jeopardize the subject and may require medical or surgical intervention to prevent one of the outcomes listed above, eg, allergic bronchospasm requiring intensive treatment in an emergency room or home, blood dyscrasias or convulsions that do not result in hospitalization, or the development of drug dependency or drug abuse.

Nonserious AEs are all AEs that do not meet the criteria for a “serious” AE.

The frequency and percentage of subjects with the following events, together with the number of events, (events listed below), will be summarized by SOC, MedDRA preferred term, severity, and treatment for each of Part 1 and Part 2 separately

- Treatment-emergent AEs (TEAEs)
- TEAEs by severity
- All AEs
- All SAEs
- TEAEs related to OPC-167832
- TEAEs related to Itraconazole
- TEAEs related to Carbamazepine
- TEAEs with an outcome of death
- Serious TEAEs
- Serious Related TEAEs
- AEs and TEAEs with a DAIDS grade ≥ 3 or severe events
- TEAEs leading to discontinuations of the IMP
- Non-serious TEAEs

Severity of AEs is graded by the Division of AIDS (DAIDS)¹ grading criteria. All AEs will be presented in a listing for each Part separately. Listings of death due to AEs, serious AEs, and AEs leading to discontinuation of the IMP (with specification of relatedness to specific IMP) will also be provided. A summary table of AEs will be presented for each part separately, containing the number and percentage of subjects experiencing the different categories of AEs, along with the number of AEs reported within each category.

10.3 Clinical Laboratory Data

Summary statistics for the clinical laboratory parameters at baseline, post-dose time points, and mean changes from baseline will be presented. The incidence of potentially clinically significant laboratory test abnormalities will be summarized for each test. Investigator assessment of clinical significance will be listed for abnormal assessments.

Quabodepistat (OPC-167832)

Study 323-201-00007

Criteria for the potentially clinically relevant laboratory test abnormalities are provided in [Appendix 2](#).

In addition, the DAIDS Adverse Event Grading Tables will be used for identifying laboratory values of potential clinical relevance ([Appendix 1](#)).

According to FDA Guidance, laboratory measurements that signal the potential for drug-induced liver injury (DILI) will be reported. An incidence table and a listing will be provided for subjects who meet the criteria for potential serious hepatotoxicity will be provided (see [Section 10.8](#)).

Scheduled assessments will be summarized in tables. Unscheduled assessments will only appear in listings and in presentations for potentially clinically laboratory test abnormalities. If a test is identified as a repeat test, the repeat test value will replace the original value.

Baseline values are Day –1 values, or, if Day –1 values are not available, then baseline values will be the values collected during the screening period.

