9.4.3.2 Clinical Laboratory Data

Descriptive statistics will be used to summarize the change from baseline for laboratory tests by treatment group for each visit. Baseline is defined as the last nonmissing value obtained at a scheduled visit on or before Day -1. If the Day -1 measurement is missing, the baseline value will be the last nonmissing measurement from the screening visit (the previous scheduled visit). The incidence of potentially clinically significant changes and abnormalities in clinical laboratory test parameters will be summarized by treatment group. Clinical laboratory test data will be presented in listings.

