10.4 Vital Sign Data

Vital signs are measured at screening, on Day –1, pre-dose on Day 1. Baseline values will be predose values taken prior to first IMP treatment on Day 1. If multiple pre-dose Day 1 values are recorded, the chronologically last recorded value prior to first IMP treatment on Day 1 will be taken to be the baseline value. If there are no pre-dose Day 1 values, then baseline values will be taken to be the last value recorded on Day –1; if Day –1 values are missing, then the last screening value will be taken to be the baseline value.

Descriptive statistics will be provided for change from baseline in vital signs parameters. Incidence of treatment-emergent potentially clinically significant vital sign results will also be summarized. Listings of potentially clinically significant abnormalities will also be provided. If vital sign assessments are repeated for the same visit, the last repeat values will be used for production of mean change from baseline. This is accomplished by sorting patient data by visit date and visit time (if applicable) within the same visit identification. Criteria for Identifying Vital Signs of Potential Clinical Relevance are provided in Appendices 2 and 3.

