Appendix 3**Criteria for Potentially Clinically Significant Vital Sign Abnormalities**

Variable	Criterion Value^a	Change Relative to Baseline^a
Heart Rate	> 110 bpm < 50 bpm	≥ 15 bpm increase ≥ 15 bpm decrease
Systolic Blood Pressure	> 160 mmHg < 90 mmHg	≥ 20 mmHg increase ≥ 20 mmHg decrease
Diastolic Blood Pressure	> 105 mmHg < 50 mmHg	≥ 15 mmHg increase ≥ 15 mmHg decrease
Weight	Not Applicable	≥ 5% increase ≥ 5% decrease
Respiratory Rate	< 12 breaths/min or > 20 breaths/min	Not Applicable
Temperature	< 36°C or > 38°C	Not Applicable

^aIn order to be identified as potentially clinically relevant, an on-treatment value must meet the “Criterion Value” and also represent a change from the subject’s baseline value of at least the magnitude shown in the “Change Relative to Baseline” column.

OPC-167832

Study 323-201-00007

Appendix 4 Definition of Grades for Vital Sign in the Division of AIDS Table¹ for Grading the Severity of Adult and Pediatric Adverse Events

The table below contains some of the criteria provided in the DAIDS table. Please see pages of the DAIDS v2.1 tables available in [Appendix 2](#) for details for blood pressure abnormalities, unintentional weight loss, fever.

Abnormality	AGE GROUP	GRADE 1 MILD	GRADE 2 MODERATE	GRADE 3 SEVERE	GRADE 4 POTENTIALLY LIFE- THREATENING
Hypertension (with the lowest reading taken after repeat testing during a visit) Male/Female	≥ 18 years of age	140 to < 160 mmHg systolic OR 90 to < 100 mmHg diastolic	≥ 160 to < 180 mmHg systolic OR ≥ 100 to < 110 mmHg diastolic	≥ 180 mmHg systolic OR ≥ 110 mmHg diastolic	Life-threatening consequences in a participant not previously diagnosed with hypertension (eg, malignant hypertension) OR hospitalization indicated
Unintentional Weight Loss (excludes postpartum weight loss)		NA	5% to < 9% loss in body weight from baseline	≥ 9% to < 20% loss in body weight from baseline	≥ 20% loss in body weight from baseline OR Aggressive intervention indicated (eg, tube feeding, total parenteral nutrition)
Fever (non-axillary temperatures only)		38.0°C to < 38.6°C or 100.4°F to < 101.5°F	≥ 38.6°C to < 39.3°C or ≥ 101.5°F to < 102.7°F	≥ 39.3°C to < 40.0°C or ≥ 102.7°F to < 104.0°F	≥ 40.0°C or ≥ 104.0°F

OPC-167832

Study 323-201-00007

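### SAP 10.3 counts laboratory abnormalities against the DAIDS table with no stated minimum grade and no comparison with baseline, so stable pre-dose values count as on-treatment incidence and worsening of an already graded value does not show

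*SAP*

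**What the plan says.** SAP 10.3 sets the count: "The incidence of potentially clinically significant laboratory test abnormalities will be summarized for each test". Two pointers supply the criteria. The first reads "Criteria for the potentially clinically relevant laboratory test abnormalities are provided in" Appendix 2, which reproduces the whole DAIDS table. The second says that "the DAIDS Adverse Event Grading Tables will be used for identifying laboratory values of potential clinical relevance", citing Appendix 1, which maps the protocol's tests to DAIDS rows. Neither the section nor Appendix 1 names a minimum grade for this count or a required change from baseline. SAP 10.3 does define a laboratory baseline (Day -1, otherwise screening), but does not link it to the incidence.

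Protocol 9.4.3.2 plans more: "The incidence of potentially clinically significant changes and abnormalities in clinical laboratory test parameters will be summarized by treatment group". The SAP sentence mentions neither changes nor treatment group. SAP section 15 (Changes in Planned Analysis) says there are none.

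The SAP treats vital signs differently. SAP 10.4 says: "Incidence of treatment-emergent potentially clinically significant vital sign results will also be summarized". The footnote to Appendix 3 requires an on-treatment value to meet the criterion "and also represent a change from the" subject's baseline, by at least the amount listed for that variable.

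**The concern.** An incidence table of on-treatment laboratory abnormalities is normally read as showing what appeared or worsened after dosing. This one is not restricted in that way. A subject who arrives with a graded value and keeps it is counted exactly like a subject whose value became abnormal on treatment. A subject who arrives at grade 1 and rises to grade 2 or 3 is already counted, so the rise leaves no trace in the count.

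Both errors matter more with 12 subjects per part, where one subject visibly moves a percentage. They could also fall on tests of interest. Protocol 2.3 reports raised total cholesterol in rats and dogs given OPC-167832, and cholesterol is a test on which an eligible subject could already have a DAIDS grade before dosing.

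**Working it through.** **Inputs.** Subjects per part: 12 (Protocol 4.1, SAP 3), with about 10 completers targeted (Protocol 9.1). Grade limits: SAP Appendix 2. Eligibility: Protocol 5.2. The documents state no laboratory incidence or baseline prevalence, so there is no figure to reproduce. Three quantities are assumed:
- p, the share of subjects with a graded pre-dose value on a given test: 5% to 30%
- r, the chance that such a value persists: 1 or 0.5
- q, the rate of new on-treatment abnormality among the rest: 10%

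**Step 1: can an eligible subject carry a graded value?** Inclusion criterion 3 asks for good health judged partly on chemistry, with no numerical limit. The only numerical exclusion on safety laboratory values is low blood counts, in Part 2 only (criterion 25). In Appendix 2, grade 1 starts at 200 mg/dL for fasting cholesterol, 150 mg/dL for fasting triglycerides and 116 mg/dL for nonfasting glucose. Appendix 1 also maps creatinine to the clearance/eGFR row, where a value below 90 is already grade 2. So yes, and a minimum grade alone would not remove every such case.

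**Step 2: weight of one subject.** 1/12 = 8.3 percentage points; with 10 completers, 1/10 = 10 points.

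**Step 3: expected effect on one test.**
- Expected number graded pre-dose = 12p
- Chance of at least one = 1 - (1 - p)^12
- Incidence as written = p·r + (1 - p)·q
- Incidence excluding persistent pre-dose values = (1 - p)·q

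With r = 1 and q = 10%:

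| p (assumed) | Expected of 12 | Chance of at least one | As written | Excluding persistent pre-dose values |
|---|---|---|---|---|
| 5% | 0.6 | 46% | 14.5% | 9.5% |
| 10% | 1.2 | 72% | 19% | 9% |
| 20% | 2.4 | 93% | 28% | 8% |
| 30% | 3.6 | 99% | 37% | 7% |

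The excess is p·r, so r = 0.5 halves it: at p = 20%, 0.10 + 0.08 = 18% against 8%. The last column sets worsening among already graded subjects to zero. Any such worsening would raise the count under a worsening rule and leave the count as written unchanged.

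**Step 4: the contrast between treatments.** Suppose the table is split by treatment as the protocol plans, and k subjects carry a persistent baseline value through both periods.
- One new case on the combination: k/12 against (k + 1)/12, a difference of 1/12, the same as under a treatment-emergent rule.
- One of the k subjects worsens on the combination: k/12 against k/12, a difference of 0. A treatment-emergent rule gives 0/12 against 1/12.

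**The case against.** The case on the other side has real force in several places.

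- A reader might infer that the SAP expressly counts any DAIDS grade. It does not say so. That reading follows from its silence and from the pointer to the full table.
- A reader might infer that the protocol makes worsening a condition for counting an abnormality. It does not. It asks for changes in addition to abnormalities, so the departure is an omission. The clearer contrast is inside the SAP, between 10.3 and the vital-sign rule.
- The SAP has no uniform treatment-emergent standard. Appendix 5 lets an ECG value count on the criterion or on the change, so an absolute value can count there too. The DAIDS creatinine row contains baseline-relative alternatives, but they are joined by OR, so an absolute value still suffices.
- The incidence table is not the only laboratory read-out. SAP 10.3 also plans mean changes from baseline and a listing of the investigator's assessments. SAP 10.8 allows for abnormal baselines in the hepatotoxicity table. Protocol 8.5.1 sends clinically significant post-screening abnormalities to the AE record, where SAP 10.2 applies a worsening rule to events continuing from baseline.
- The cholesterol and triglyceride limits are fasting rows, and the documents require a fast only around the OPC-167832 doses. Whether those rows apply at every draw is not established. The nonfasting glucose row does not depend on this.

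All of this stands, and it limits the size and reach of the point. None of it supplies the missing rule for the general laboratory incidence.

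**Conclusion.** The point holds as a gap in the SAP's definition of one table. SAP 10.3 gives no minimum grade and no baseline comparison, leaves out two elements of Protocol 9.4.3.2 without declaring a change, and differs from the SAP's own vital-sign rule. Each persistent pre-dose case adds 8.3 percentage points to its test. At the assumed 5% to 30%, 0.6 to 3.6 of 12 subjects per test would carry a graded pre-dose value; all of them inflate the count only if every such value persists.

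Two stronger conclusions are tempting but unsupported. One is that persistent baseline values hide a real increase with itraconazole or carbamazepine. In a fixed-sequence design they enter both columns, so a new case still shows in full; only worsening in an already graded subject is lost. The other is that such a subject is counted at every post-dose visit. The SAP says the incidence is given for each test and does not mention visits.

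The table is descriptive and serves a secondary safety objective; the primary PK analysis is unaffected. It is still worth changing, because the remedy is specific and uses data already collected.

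**What to change.** In SAP 10.3, summarise by treatment group the incidence of treatment-emergent laboratory abnormalities, defined as a post-dose DAIDS grade higher than the subject's grade at the baseline already defined in that section. Add a table of shifts from baseline grade to worst post-dose grade for each test that has a DAIDS row in Appendix 1. The count of all abnormalities may stay alongside, labelled as including pre-existing values; keeping it also respects the protocol's wording, which moving unchanged abnormalities to listings alone would not.

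The cost is SAP text and a little extra programming, with no new data. Reported counts will be lower for tests where baseline abnormalities are common, and the drop may be more than slight.
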